1.0 Introduction

1.1 Breast Cancer Background

In 2012, an estimated 227,000 women in the US were expected to be diagnosed with invasive breast cancer, with breast cancer remaining second only to lung cancer as the most common cause of cancer related death in women [1]. Diagnosis is made by core needle biopsy of a palpable mass or abnormality on mammogram. Definitive treatment consists of surgical resection with staging of the axilla. Chemotherapy is reserved for advanced cases and can be administered in the adjuvant or neoadjuvant setting. Patients with estrogen receptor positive breast cancer have relatively worse neoadjuvant specific outcomes in terms of clinical and pathologic response compared to other types of breast cancer, making this an important group for receptor targeted therapy [2].

1.2 Tyrosine Kinase Inhibitor Background

The receptor tyrosine kinases (RTK) are a family of molecules involved in receiving hormonal and chemokine signals and starting signal transduction pathways often involved in growth, cell survival, and proliferation. Activating mutations of RTK's have been identified in a wide variety of cancers including gastrointestinal stromal tumors (GIST), chronic myelogenous leukemia (CML) and medullary thyroid cancer (MTC), among others. Tyrosine kinase inhibitor (TKI) therapy has provided promising new targeted treatments for cancers driven by RTK activation.

The tyrosine kinase expression profile of breast cancers is a relatively new field. Since bevacizumab was developed, study of tyrosine kinase inhibition has focused on VEGFR antagonism and EGFR. More recently, expression of RET has been discovered in breast cancers with an association with estrogen receptor expression [3-6]. Mutations of the RET proto-oncogene are well described in MTC and the multiple endocrine neoplasia (MEN) 2 syndromes. Trials have been conducted in breast cancer with multiple TKI's without significant efficacy [7, 8]. However, these trials have focused primarily on ER negative cancers which express low levels of RET relative to estrogen receptor positive tumors, and metastatic tumors which are more likely to be ER negative.

In vitro, blocking RET activation, either by reducing protein levels, or with pharmacologic inhibition, leads to decreased activation of cellular mediators of proliferation and growth including ERK1/2 and AKT [9, 10]. Further it has been shown that inhibiting RET activation can restore sensitivity to Tamoxifen, prevent Tamoxifen resistance, and decrease cell proliferation in an ER and RET expressing breast cancer cell line [6]. Further, RET expression is a negative prognostic indicator in breast cancer [11]. We hypothesize that Vandetanib will be more efficacious in treating RET expressing breast cancers compared to breast cancers expressing lower levels of RET. Although there is a subset of ER-negative RET expressing tumors, most expression is associated with ER, making that the most likely phenotype to benefit from RET antagonist therapy.

1.3 Rationale of Proposed Trial

Our unpublished data show that *in vitro* activation of RET by its ligand, GDNF, leads to phosphorylation of ERK1/2 and AKT and leads to an increase in proliferation. Pharmacologic inhibition with Sunitinib, a small molecule tyrosine kinase inhibitor with activity against RET, abrogates GDNF/RET dependent ERK1/2 and AKT activation. Further it results in decreased proliferation, which FACS analysis for Ki-67 and cleaved caspase 3 demonstrate is the result of a modest reduction in proliferation and a large induction of apoptosis. Oral treatment with Sunitinib reduces human luminal breast cancer tumorigenesis in a xenograft model and immunohistochemistry analysis demonstrates a similar effect of a small reduction in Ki-67 positivity with a large induction of apoptosis. Vandetanib, another TKI with higher activity on RET than Sunitinib, similarly

reduces tumorigenesis and slows growth of previously formed xenograft tumors. Additionally, effects on proliferation are additive when combined with tamoxifen treatment, with the additional effect of inducing apoptosis compared to Tamoxifen treatment alone, indicated a separation of pathways and a role for combination therapy. In fact, treatment with the antiestrogen fulvestrant has been shown enhance Vandetanib effects in non-small cell lung cancer indicating a role for TKI and antiestrogen dual treatment to prevent pathway cross talk [12]. To corroborate these data in primary tumors we have obtained tissue samples and have shown that TKI treatment can decrease activated ERK1/2 in primary breast cancers with an increased effect in ER positive tumors. Our further study will include determining a more specific receptor expression profile that will predict TKI responsiveness (Unpublished data).

In the proposed trial women will be offered enrollment after core breast biopsy demonstrates invasive breast cancer, for which subsequent surgical resection typically occurs several weeks after the initial biopsy. Patients will be evaluated in the surgery clinic per normal protocol and if eligible and consenting enrolled in this trial. They will proceed with the normal course of treatment, with the only modification due to study enrollment being randomization to take either Vandetanib, 300 mg by mouth once daily, or placebo for 7 to 14 days prior to surgery. Paired baseline (diagnostic core biopsy) and endpoint tumor samples (surgical resection) will then be available for analysis. Randomization and blinding protocol is described in section 7.0.

Tissue markers would be analyzed on each of these samples allowing for rapid assessment of *in vivo* response to TKI treatment. In this initial evaluation, tissue levels of RET, Ki-67, TUNEL, phosphorylation specific levels of ERK1/2, AKT, and mTOR will be assessed. This will provide information on the primary endpoint of down regulation of Ki-67 expression. Additionally, proliferation and apoptosis markers were selected to assess the *in vivo* impact of TKI treatment on these carcinogenic mechanisms. Ki-67, a proliferation gene is weighted heavily in the multi-gene assay described by Paik et al which is used with increasing frequency clinically [13]. TUNEL is an apoptosis marker. Our pre-clinical studies indicate an effect of tyrosine kinase inhibition on both Ki-67 and TUNEL in luminal breast cancer.

Evaluation of paired tumor samples following a brief treatment course has been described in multiple studies and is appealing for several reasons.[14-18] Trials using mortality or disease progression as endpoints often require long follow-up, large study enrollment and significant resources. The proposed design, in contrast, permits relatively rapid evaluation of a drug's *in vivo* mechanism of action and impact. Promising agents could then be studied in larger, longer term trials. Paired baseline-to-endpoint samples can also be analyzed for their impact on individual patients and smaller subgroups. Evaluation of these subgroups and comparison with their counterparts might provide biochemical clues to support these observations. Tissue samples may be saved and used for subsequent unplanned analysis, should other studies support reevaluation using different markers. Finally, patients enrolled in this study would not need additional invasive procedures, as these samples will be obtained as part of standard treatment for invasive breast cancer.

The treatment dose will be Vandetanib 300 mg orally, one time each day. Currently, the FDA has approved 300 mg orally for treatment of medullary thyroid cancer, which also has been determined to be a safe dose in breast cancer [19]. Vandetanib, at this dose, was selected to demonstrate tumor change in the brief interval between diagnostic biopsy and surgical resection. AstraZeneca has agreed to provide Vandetanib and placebo at no cost for this trial.

2.0 Study Objectives

- 2.1 Determine the change in Ki-67 expression on paired samples obtained before and after Vandetanib treatment.
- 2.2 Compare TUNEL levels and phosphorylation specific levels of ERK1/2, AKT, and mTOR levels in paired samples obtained before and after Vandetanib treatment.
- 2.3 Evaluate any differences in analyses 2.1 and 2.2 based on level of RET expression as well as between ER-positive and ER-negative tumors.

3.0 On-Study Guidelines

This clinical trial can fulfill its objectives only if patients appropriate for the trial are enrolled. All relevant medical and other considerations should be taken into account when deciding whether this protocol is appropriate for a particular patient. Physicians should consider the risks and benefits of any therapy and, therefore, only enroll patients for which the agents administered are appropriate. Although they will not be considered as formal eligibility criteria, as part of this decision-making process physicians should recognize that the following may increase the risk to the patient entering this protocol:

- 3.0.1 A psychiatric condition which would prevent compliance with treatment or informed consent.
- 3.0.2 Liver disease, diabetes, pulmonary disease, or infection, which in the opinion of the treating physician would make this protocol treatment unreasonably hazardous for the patient.
- 3.0.3 Patients with a “currently active” second malignancy other than non-melanoma skin cancers. Patients are not considered to have a “currently active” malignancy if they have completed therapy and considered by their physician to be at less than 30% risk of relapse within one year.
- 3.0.4 Patients who have received any investigational agent within the prior 4 weeks.

4.0 Eligibility Criteria:/Definitions of Disease:

4.0.1. Patients with core breast biopsy that, on pathology review, demonstrates invasive breast cancer and are determined to need surgical excision of the lesion. All subtypes of invasive breast cancer will be enrolled. Core biopsy specimens of enrolled patients will be stained for RET by immunohistochemistry and scored, however, patients will not be excluded according to RET expression.

4.1 Eligibility Criteria:

4.1.1 Inclusion Criteria

- Female gender. There is an incidence of male breast cancer, but it is unclear if the etiology is the same and inclusion of males could confound results.
- Age ≥ 18 . Breast cancer, while not restricted only to adult women, is rare in the younger population.
- ECOG performance status ≤ 2 .
- Life expectancy of greater than 6 months.
- Ability and willingness to provide informed consent to participate in this study.

4.1.2 Exclusion Criteria

- Prolonged QT interval (QTc > 480 milliseconds) on screening EKG or congenital long QT syndrome
- Any concomitant medications that are known to be associated with Torsades de Pointes or QT elongation (see appendix 2).
- Hypertension not controlled by medical therapy (systolic BP greater than 160 millimeters of mercury [mmHg] or diastolic blood pressure greater than 100 mmHg).
- Patients taking metformin or digoxin.

- History of arrhythmia (multifocal premature ventricular contractions, bigeminy, trigeminy, ventricular tachycardia), which is symptomatic or requires treatment (CTCAE Grade 3), symptomatic or uncontrolled atrial fibrillation despite treatment, or asymptomatic sustained ventricular tachycardia. Patients with atrial fibrillation controlled by medication are permitted.
- Significant cardiac event (e.g., myocardial infarction), superior vena cava syndrome, New York Heart Association (NYHA) classification of heart disease ≥ 2 within 12 weeks, or presence of cardiac disease that in the opinion of the Investigator increases the risk of ventricular arrhythmia.
- Serum calcium or magnesium outside the institutional range of normal.
- Serum Potassium < 4.0 mmol/L or above 5.0 mmol/L
- Creatinine clearance < 50 ml/min
- PT > 12 seconds or PTT > 31 seconds
- Platelet count of $< 100,000$
- Serum bilirubin greater than 1.5 mg/dl
- Alanine aminotransferase (ALT) > 50 U/L, aspartate aminotransferase (AST) > 65 U/L, or alkaline phosphatase (ALP) > 250 U/L
- Any cytotoxic treatments, such as neoadjuvant chemotherapy, planned before subsequent surgical procedure.
- Previous exposure to Vandetanib
- Previous enrollment or randomization in this study
- Involvement in the planning and/or conduct of the study (applies to both AstraZeneca staff and staff at UIHC).
- Previous or current malignancies of other histologies within the last 5 years, with the exception of in situ carcinoma of the cervix, and adequately treated basal cell or squamous cell carcinoma of the skin.
- Patients who have received prior surgical site radiation.
- Patients on CYP3A4 inhibitors or inducers (see appendix 1).
- Inability to test core biopsy for study markers
- Pregnancy or lactation at the time of study entry. (***Note: Pregnancy testing must be performed within 2 weeks prior to randomization according to institutional standards for women of childbearing potential.***)

Patients who fail to meet the inclusion/exclusion criteria should not, under any circumstances, be enrolled or receive study medication. There can be no exceptions to this rule.

Where patients that do not meet the inclusion criteria are enrolled in error or incorrectly started on treatment, or where patients subsequently fail to meet the study criteria post initiation, the Investigator should inform the Study Physician, [name], immediately.

4.2 Inclusion of Minorities

Although there is no evidence to suggest that the outcome will differ by ethnicity and there is insufficient power to detect small or moderate effects, we will, in a secondary analysis, report the results by ethnicity.

4.3 Sample Size

This study will aim to accrue a total of 40 subjects with invasive breast cancer into both the placebo and treatment arms (80 patients in total). The diagnosis will be based on histopathological evidence. The number of subjects was chosen based on the estimated ability to provide meaningful information on breast cancer. For discussion of statistics and power analyses, please see Section 12.

4.4 Informed Consent

Signed informed consent for enrollment in this protocol will be obtained from eligible subjects by a member of the research team before the start of the study. Subjects will be fully informed of the purpose and potential risks and benefits of participating in the study. Subjects will have the opportunity to have questions answered to their satisfaction before signing the consent.

4.5 Contacting Subjects for Consent

Patients will be identified for potential study enrollment at the time they are scheduled for a surgery clinic visit for a preoperative evaluation for invasive breast cancer. The study will be reviewed and patients enrolled at the time of their preoperative visit. Some patients will be seen in clinic before they receive the information regarding the study. These patients will be given the opportunity to participate and will have a study related discussion at their clinic visit. All patients seen in breast surgery clinic will be screened by the providing surgeon for potential involvement in this study.

5.0 Schedule of Assessments and Procedures

	Baseline (Pre-operative clinic visit)	Day 7-14	Post-Treatment safety assessment visit (Day 13 or 14)	Post-treatment sample	Follow-up visit POD 7-14
Tests & Observations					
History	X				X
Age/ECOG PS	X				
Physical Examination	X				X
Pulse, Blood Pressure	X		X		X
Weight/Height	X				
Drug Toxicity Evaluation		X	X		X
Study Drug Calendar		X	X		
EKG	X		X		
Pregnancy test within 2weeks of treatment (urine or serum)	X				
Laboratory Studies					
Ca, Mg, K, Cr, PT, PTT, Bilirubin, AST, ALT, Alk Phos, CBC	X				
Ca, Mg, K, platelets			X		
Treatment					
Placebo/Vandetanib 300 mg daily		X			
Staging Evaluations					
Pathologic Tumor Size				X	
Histology	X			X	
Tumor markers ¹	X			X	
Elston-Ellis Grade ²	X			X	
Lymph node status ³	X (CLINICAL)			X (PATHOLOGIC)	

Note: Staging determinants can be obtained on the baseline or post-treatment sample. They do not need to be obtained on both, but should reflect the final conclusions of the pathologist.

¹ Tumor markers are Estrogen Receptor, Progesterone Receptor and Her2/neu. See Section 9.2.

² Eliston-Ellis Grade is a pathological term for tumor aggression.

³ Lymph node status will be recorded in accordance with preoperative (clinical) and postoperative (pathologic) staging.

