The major toxicities of Vandetanib are nausea/vomiting/diarrhea, hypertension, thrombocytopenia, prolonged QT interval, Torsades de pointes, and ventricular tachycardia. The patients will be carefully screened for any conduction abnormalities, arrhythmia, electrolyte/coagulation/platelet abnormalities, and medications in Appendix 2 associated with QT prolongation. The short duration of treatment, two weeks, should limit toxicity. Detailed description of toxicities is provided in sections 11.2.3 and 11.2.4.

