10.0 Removal of Subjects from Protocol Therapy

10.1 Duration of Treatment

Subjects will continue vandetanib or placebo up to and including the morning of surgery for a total of 7 to 14 days. The time frame from preoperative clinic visit until definitive surgery will be a minimum of 2 weeks and the maximum of 4 weeks. Subjects with an adverse reaction of CTCAE grade III or higher will discontinue the study drug. Subjects can voluntarily discontinue the drug at any time during the trial, be removed from the drug at the discretion of their treating physician, or be discontinued by the study investigators. In previous trials with vandetanib, surveillance labs and toxicity assessment has been performed at two weeks of treatment, which will be done in this trial with the preoperative safety assessment. Because subjects will have already discontinued the study drug at that time it will not be possible to discontinue the study drug early based on that assessment. Due to the short duration of treatment in this trial and the low incidence of adverse reactions over that time frame in previous phase I and II trials we do not expect a significant number of severe adverse reactions. Subjects will be evaluated for study withdrawal if noncompliant with requirement for therapy, or if they are experiencing drug related toxicity. If the date of surgery is unexpectedly changed after initiation of treatment, the patient will continue treatment, including the morning of surgery, for not more than 28 total days.

10.2 Extraordinary Medical Circumstances:

If at any time the constraints of this protocol are detrimental to the subject's health and/or the subject no longer wishes to continue protocol therapy, remove the subject from the protocol treatment. In this event:

- Document the reason(s) for ending treatment on the follow-up form.
- The primary outcomes of response of down regulation of Ki-67 and secondary outcomes of evaluation of tumor markers in the baseline and endpoint tissue samples will be analyzed unless the subject withdraws consent to do so.

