- Outcome of pregnancy (i.e., full-term, premature birth, spontaneous miscarriage, elective termination. If premature birth, specify gestational age in weeks. If elective abortion, specify if any medical reason.)
- Details of birth (i.e., DOB, weight, sex, healthy baby, sick baby, congenital anomaly/birth defect, still birth, multiple births, sickness manifestations, etc.)
- Any complications, infections, illness during pregnancy

The most common side effects seen in patients treated with Vandetanib included the following:

Risks for Vandetanib

Very Common (experienced by more than 10% of patients taking Vandetanib)

Headache
Diarrhea
Nausea/vomiting
Constipation
Decreased appetite,
Rash
Dry skin
Hypertension
Trouble sleeping
Weakness
Fatigue

Common (Experienced by 1 – 10% of patients taking Vandetanib)

QTc prolongation
Abnormal taste in mouth
Abdominal pain
Mouth swelling
Dry mouth
Weight loss
Elevated liver function tests
Anorexia
Hypokalemia
Hypocalcemia
Dehydration
Hypomagnesemia
Skin changes
Acne
Hair loss
Nail disorders
Mild nose bleed
Proteinuria
Kidney stone
Visual problems
Depression
Anxiety

Uncommon (Experienced by fewer than 1% of patients taking vandetanib)

Heart failure
Chest pain
Pancreatitis
Thrombocytopenia
Severe skin disorder
Seizure
Shortness of breath
Hypokalemia

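### Cheap safety improvement, low severity: the Section 5.0 schedule has no liver test after the first dose, so a symptom-free elevation on study drug would be found only by unscheduled testing

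*Combined protocol and SAP*

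**What the plan says.** Section 5.0 has two laboratory rows. The baseline row is "Ca, Mg, K, Cr, PT, PTT, Bilirubin, AST, ALT, Alk Phos, CBC". The row for the post-treatment safety visit is "Ca, Mg, K, platelets". No laboratory test is marked for the post-operative visit.

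The risk list at the end of Section 11.2.4, repeated in Appendix 5, places "Elevated liver function tests" in its 1 to 10% group. Thrombocytopenia, which is tested after dosing, is in the group headed "Experienced by fewer than 1% of patients taking vandetanib".

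Section 7.1 names the major toxicities as gastrointestinal effects plus "hypertension, thrombocytopenia, prolonged QT interval, Torsades de pointes, and ventricular tachycardia", and adds: "The short duration of treatment, two weeks, should limit toxicity". Section 10.1 expects few severe reactions because of the short course and "the low incidence of adverse reactions over that time frame in previous phase I and II trials". The same section ties the preoperative visit to earlier vandetanib trials, in which "surveillance labs and toxicity assessment has been performed at two weeks of treatment, which will be done in this trial".

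Section 6.0 calls for laboratory work and an EKG on the day before or the morning of surgery, with the results reviewed before the operation and paid for by the PI. It names no analytes. Section 4.1.2 excludes patients with ALT above 50, AST above 65 or ALP above 250 U/L, or bilirubin above 1.5 mg/dl.

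**The concern.** The protocol treats the liver as relevant to safety in two places: it screens on four liver tests at entry, and it lists their elevation as a common toxicity. It then schedules no liver test once the drug has been given. Section 11.2.1 counts an abnormal laboratory finding as an adverse event, but a silent one cannot be recorded, followed under Section 11.2.3, or seen in the trend review of Appendix 5 unless somebody measures it.

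At stake are the completeness of the safety data and of the preoperative review. The primary endpoint is not at stake. Liver tests stand out among the listed risks because every patient already has a baseline value and blood is already drawn at the right visit. Proteinuria, also listed at 1 to 10%, has no baseline and would need a new specimen.

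**Working it through.** The plan gives no liver-specific figure to reproduce. The listed 1 to 10% is a label without exposure time, grade or placebo rate. The check is a comparison of sections, followed by simple arithmetic on scale.

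**Is a liver test scheduled anywhere after dosing?**

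| Place | Liver tests |
|---|---|
| Section 5.0, baseline | AST, ALT, alkaline phosphatase, bilirubin |
| Section 5.0, post-treatment visit | none |
| Section 5.0, post-operative visit | no laboratory row |
| Section 6.0, preoperative laboratory work | analytes not named |
| Section 10.1, surveillance laboratory work | analytes not named |
| Section 11.2.3, toxicity management | rules for QTc, gastrointestinal, skin and blood pressure toxicity; none for the liver |
| Appendix 3, preoperative flowchart | content not visible |

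Section 6.0 could be read as repeating the whole baseline panel, but the schedule defines a shorter one. The finding is therefore about the Section 5.0 schedule.

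**How many cases could be involved?** Inputs: 40 vandetanib patients (Section 4.3) and the listed 1 to 10% (Section 11.2.4). Assume, probably too generously, that the listed rate applies in full to 7 to 14 days of dosing:

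- 40 × 0.01 = 0.4
- 40 × 0.10 = 4

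This is for scale only. The true number may be near zero, and the documents do not say what share of elevations is symptom-free.

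**What would testing buy?** With n patients tested and no elevation found, the exact one-sided 95% upper limit on incidence is 1 − 0.05^(1/n):

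- n = 40: 1 − 0.05^(1/40) = 0.072, or 7.2%
- n = 35 (the evaluable number in Section 12.0): 1 − 0.05^(1/35) = 0.082, or 8.2%

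These limits describe incidence over this trial's own exposure and hold only if no event is seen. With no planned on-drug value, the schedule supports no such statement.

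**How much follow-up would it generate?** Assume that up to 10% of patients in both arms have an abnormal value (the documents give no placebo rate): 80 × 0.10 = at most 8 repeat draws.

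**Does it touch the main analysis?** No. The power statements in Section 12.0 rest on the Ki-67 standard deviation, the difference sought and the number of patients, and none of these changes.

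**The case against.** The strongest reply is that the short panel is a reasoned choice. Calcium, magnesium, potassium, platelets, blood pressure and EKG line up with the major toxicities of Section 7.1, which do not include the liver. Entry limits already remove patients with raised liver tests, and the protocol explains why it expects little toxicity. Symptomatic toxicity is covered by evaluations at three points in the schedule. By the preoperative visit at most one dose normally remains, so a result would hardly alter dosing. No objective in Section 2.0 concerns safety incidence, and no between-arm safety test is planned. All of this stands, and it is why the point is optional. It leaves silent elevations unmeasured.

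The possible extension to 28 days in Section 10.1 goes beyond the two weeks on which Section 7.1 relies. It applies only when surgery is unexpectedly moved, and no frequency is given, so it adds little weight.

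A reader might infer more than the documents support:

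- *That the plan contradicts itself by testing a toxicity listed below 1% and not one listed at 1 to 10%.* Thrombocytopenia is a named major toxicity and bears on surgery, so testing it is reasonable.
- *That the instruction in Section 11.2.3 to note toxicity of every grade requires a liver test.* It governs toxicity that is found and does not call for a test of every listed risk.
- *That a 7.2% limit would rule out the upper part of the listed 1 to 10%.* The two are not comparable: one would refer to 7 to 14 days here, the other has no stated exposure, grade or placebo rate.
- *That no vandetanib patient will have an on-drug liver value.* Unscheduled tests are possible and Appendix 3 is unseen. The supportable statement is that the visible schedule plans none.

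**Conclusion.** The point holds as a low-severity improvement to patient safety, not as a defect. In the visible schedule the four liver tests appear at baseline only, so a symptom-free elevation would be missed unless someone tests outside the schedule. How many that would be is unknown; the range of 0.4 to 4 in 40 depends wholly on carrying the listed rate over to a short course. The gain is a planned on-drug value for each patient who attends, the chance to follow abnormal ones, and a limit on incidence for this exposure, which would be 7.2% if none of 40 were elevated. Ki-67, power and sample size are unaffected, and dosing essentially so. If Appendix 3 or the intended meaning of Section 6.0 already includes liver tests, a one-line clarification of Section 5.0 is enough.

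**What to change.** Extend the post-treatment laboratory row in Section 5.0 with AST, ALT, alkaline phosphatase and bilirubin, on the draw already planned. Then:

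- Review the results with the others under Section 6.0. Discuss a value above the Section 4.1.2 entry limit with the attending surgeon; it does not by itself delay surgery.
- Repeat values that are abnormal and worse than baseline at the existing post-operative visit. Follow drug-related abnormalities under Section 11.2.3, including its 30-day visit if unresolved.
- After the package key is released, report CTCAE v4 graded shifts from baseline by arm. Comparison with baseline is needed because the entry limits are fixed cut-offs that the protocol does not describe as the normal range.

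The cost is four extra analytes for up to 80 patients. The documents give no price, so cheap here means no extra visit or procedure for patients with normal results. The extra results must be read just before surgery, sometimes on the same morning, and some will be incidental. Abnormal values bring repeat draws (at most 8 of 80 under the assumption above) and possibly 30-day visits. Under Table I of Section 11.2.4, Grade 1 and 2 events judged at least possibly related go to the CRSO. While the trial is blinded, that reporting work would arise in both arms.
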